6.2 Missing data

The number and percentage of participants with missing outcome data (all primary and secondary outcomes) at the 3-month and 6-month visits will be reported for each group. See **Section 6.1** for details on multiple imputation for missing values. We will assume that data are missing at random (MAR).

6.3 Additional analyses

No additional analyses are planned.

6.4 Harms

Study medication discontinuation

We will report the number and percentage of patients who discontinue the study medication by group, as study medication discontinuation can suggest that the drug is poorly tolerated.

In addition, we will report the number and percentage of participants who experience the following side effects which are assessed using standardized case report forms at the 3-month and 6-month follow-up visits.

Minor side-effects

In rare cases, curcumin has been reported to cause minor nausea, headache, diarrhea, yellow stool, temporary giddiness, localized swelling of the skin (contact dermatitis), or hives (urticaria). The number and percentage of patients who experience each of these side effects will be reported by treatment group, and the number of minor side effects experienced by each patient will be summarized by group. For each minor side-effect, a Chi-squared test will be used to test whether the percentage of patients experiencing the minor side-effect is equal between groups; P values will be tested at the 0.05 significance level.⁴¹

Bleeding

In the 1990s, two studies described curcumin's *in vitro* activity against platelet function.^{42,43} Further *in vitro* work has since identified curcumin's ability to inhibit platelet activation, which could increase the risk of bleeding.⁴⁴⁻⁴⁸ However, when applied in animal models, curcumin appears to have no effect on clinically relevant bleeding,⁴⁹⁻⁵³ and in a recent study of oral curcumin loading immediately prior to abdominal aortic aneurysm repair, no significant risk of bleeding was identified.⁵⁴ The number and percentage of patients experiencing a bleeding event during the course of the study will be reported by treatment group. A Chi-squared test will be used to test whether the percentage of patients experiencing at least one bleeding event is equal between groups; P values will be tested at the 0.05 significance level.⁴¹

Hypoglycemia

Curcumin is a potent inhibitor of CYP2C9, which could increase the pharmacologic effects of some anti-diabetic medications such as sulfonylureas.⁵⁵ Although curcumin has been studied extensively in the

setting of diabetes and found to have a low risk of hypoglycemia,⁵⁶ we will collect data on this potential adverse event and report the risk by treatment group. A Chi-squared test will be used to test whether the percentage of patients with diabetes pre-randomization experiencing at least one hypoglycemic event in follow-up is equal between groups; P values will be tested at the 0.05 significance level.⁴¹

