In our preliminary work on urinary albumin-to-creatinine ratio testing, we found patients eligible for MPAC-CKD-1 had a mean initial urinary albumin-to-creatinine ratio of 128.3 mg/mmol.²⁶ Over 3 months, we observed a mean increase in the urinary albumin-to-creatinine ratio of 30.7 mg/mmol and found the standard deviation of the change to be 69.2 mg/mmol. Enrolling a total of 518 patients and

accounting for 5% loss to follow-up allows for 82% power ($\alpha = 0.025$) to detect a geometric mean ratio of 0.75, assuming a standard deviation of the 6-month log-transformed albumin-to-creatinine ratio of 1.0.²⁷ For the between-group difference in change in eGFR (6-month eGFR minus pre-randomization eGFR), we will have 81% power ($\alpha = 0.025$) to exclude a difference of 1.65 mL/min per 1.73 m² between treatment and control groups (using a standard deviation of the change of 5.8 mL/min per 1.73 m²). In general, the average decline in eGFR in albuminuric CKD patients is 2 to 4 mL/min per 1.73 m² per year (with a standard deviation of 3-4 mL/min per 1.73 m² per year).^{28,29} The standard deviations used in these sample size calculations are based on overall standard deviations observed in the MPAC-CKD-1 study.

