	Known allergy to ingredients of the study product or placebo [microcrystalline cellulose, vegetarian capsule (carbohydrate gum [cellulose], purified water), vegetable grade magnesium stearate (lubricant), silica]	
	Pregnant or breastfeeding	
	Women of childbearing potential	Operational definition: Women of child bearing potential are those who are not either surgically sterile (bilateral tubal ligation, hysterectomy, bilateral salpingo-oophorectomy) or not postmenopausal for at least 1 year
	Plans for transplantation during the study period	Operational definition: Patients who have completed a transplant recipient work-up or who are active on the renal transplant list
	Receipt of hemodialysis or peritoneal dialysis in the past 3 months	
	Active peptic ulcer disease	Operational definition: Active peptic ulcer disease includes patients who are: i. Currently receiving H.pylori eradication therapy or have received it in the past 30 days (H.pylori eradication therapy is combination therapy with a proton pump inhibitor [lansoprazole 30 mg twice daily, omeprazole 20 mg twice daily, pantoprazole 40 mg twice daily, rabeprazole 20 mg twice daily, or esomeprazole 40 mg once daily], amoxicillin [1 g twice daily], and clarithromycin [500 mg twice daily] for 7 to 14 days) ii. Awaiting upper endoscopy

		(esophagogastroduodenoscopy) for the diagnosis of epigastric pain. iii. Experiencing ulcer-like dyspepsia (moderate to severe epigastric pain that worsens with eating or regularly occurs two to five hours after meals) that is not otherwise diagnosed.
	Hepatobiliary disease in the past 4 weeks (biliary obstruction, cholecystitis)	Operational definition: i. Patients with biliary obstruction includes those with a diagnosis of obstruction ii. Patients with cholecystitis include those with diagnosed cholecystitis and those with suspected cholecystitis (right upper quadrant abdominal pain that may radiate to the back or right shoulder that lasts four to six hours and may be exacerbated by ingestion of fatty foods)
	Evidence of acute kidney injury (>50% increase in serum creatinine in the past 30 days)	
	History of significant bleeding	Operational definition: gastrointestinal or retroperitoneal bleed requiring transfusion, or any intracranial hemorrhage in the last 6 months
	Ongoing use of warfarin	
	Ongoing chemotherapy treatment with cyclophosphamide, camptothecin, mechlorethamine or doxorubicin	

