	Ongoing use of anti-psychotic including haloperidol, aripiprazole, risperidone, ziprasidone, pimozide, and quetiapine	
	Previous participation in MPAC-CKD-1	
	Current participation in another investigational medication trial	

Abbreviations: ACE angiotensin converting enzyme; ACR albumin-to-creatinine ratio; ARB angiotensin receptor blocker; CKD chronic kidney disease

Table 2. Pre-randomization/pre-treatment participant characteristics

Participant characteristic	Summary measure
Age at recruitment, years	mean (SD)
Male	n (%)
Height, cm	mean (SD)
Weight, kg	mean (SD)
Body mass index, kg/m ²	mean (SD)
Body mass index categories, kg/m²	n (%)
< 25 kg/m ²	
25-29 kg/m ²	
30-34 kg/m ²	
≥ 35 kg/m ²	
Systolic blood pressure, mmHg	mean (SD)
Diastolic blood pressure, mmHg	mean (SD)
Serum creatinine, µmol/L	mean (SD)
eGFR, mL/min per 1.73m ² ^a	mean (SD)
eGFR categories, mL/min per 1.73m²^a	n (%)
45-60	
30-44	
< 30	
Urinary albumin to creatinine ratio, mg/mmol	mean (SD)
Race/ethnicity	n (%)
White/Caucasian	
Black/African American/African Canadian	
Hispanic/Latino	
Asian (Far East, Southeast Asia, Indian Subcontinent)	
Middle East	
Aboriginal/Native Persons/American Indian	
Other	
Diabetes	n (%)
HbA1c	mean (SD)
Insulin use	n (%)
Oral hypoglycemic	
Insulin or oral hypoglycemic	
History of smoking	n (%)
Current	
Remote ^b	
No	
Primary cause of CKD	n (%)
Diabetic nephropathy	
Glomerulonephritis	
Hypertensive nephrosclerosis	
Polycystic kidney disease	
Other	
Medication use	n (%)
ACE inhibitors	
Angiotensin II receptor blockers (ARBs)	
ACE inhibitors or ARBs	
Diuretics	
Calcium channel blockers	
Beta blockers	
Aspirin	
Antiplatelet drugs (not including aspirin)	
Anti-inflammatories (regularly scheduled use)	
Oral glucocorticoids	
Cholesterol lowering medications (niacin, fibrates, statins)	
Opioid analgesic	

Non-warfarin anticoagulant	
----------------------------	--

^a CKD-EPI eGFR equation.³⁴

^b Smoker within the last 10 years, but not currently smoking.

Micro-Particle Curcumin for the Treatment of Chronic Kidney Disease-1 (MPAC-CKD-1)

Statistical Analysis Plan (SAP)

Supplemental Document

Supplemental Table 1. Changes to the published MPAC-CKD-1 protocol ([name] et al. *Can J Kidney Health Dis.* 2018;5:1-9)

Published protocol	Change in SAP	Reason for change

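### Bleeding is analyzed only as at least one undefined event per patient, so an excess of serious bleeds could be masked by minor ones

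*Combined protocol and SAP*

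**What the plan says.** SAP 6.4 Harms treats bleeding under its own subheading. It cites laboratory evidence that curcumin inhibits platelets and sets against it animal work in which "curcumin appears to have no effect on clinically relevant bleeding", together with a surgical trial that found no significant bleeding risk.

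The planned output is one binary variable per patient. On reporting, the SAP says: "The number and percentage of patients experiencing a bleeding event during the course of the study will be reported by treatment group". The arms are then compared on that same yes/no variable by chi-squared, at an unadjusted level of 0.05. The term is not defined, and no grade, site, transfusion need or seriousness category is given.

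Three other places bear on the point:

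- SAP Supplemental Table 1 lists bleeding, without qualification, as one of three safety-related outcomes.
- SAP 6.3 says that nothing further is planned. The supplied SAP contains no table of serious adverse events.
- SAP Table 1 does define significant bleeding, but only as an exclusion criterion: "gastrointestinal or retroperitoneal bleed requiring transfusion, or any intracranial hemorrhage in the last 6 months".

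**The concern.** The reassurance in SAP 6.4 is about clinically relevant bleeding, but the planned analysis does not isolate clinically relevant bleeds. The trial has a written threshold for a significant bleed and applies it at entry only, not to what happens on treatment.

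Some background of minor bleeding is plausible. Warfarin is an exclusion, but SAP Table 2 tabulates aspirin, other antiplatelet drugs and non-warfarin anticoagulants at baseline. It is reasonable to infer that users of these drugs could enroll, although Table 2 does not state it as a permission.

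Two errors of interpretation are possible. The report could state no difference in bleeding although the serious bleeds lay mostly on one arm. Conversely, a difference confined to minor bleeds could be reported simply as bleeding. Both matter because the published protocol (Secondary outcomes, on discontinuation and safety) says that tolerability in this trial may inform a larger one.

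**Working it through.** **Inputs from the documents.** SAP 3.3: "Enrolling a total of 518 patients", and SAP 3.1 gives 1:1 allocation, hence 518/2 = 259 per arm. SAP 6.4: Pearson chi-squared at 0.05, taken as two-sided. The documents give no bleeding rate, effect size or power, so there is no bleeding figure to reproduce. Every bleeding rate below is an assumption.

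**Check on the sample size.** SAP 3.3 states that "accounting for 5% loss to follow-up allows for 82% power" for the albumin-to-creatinine ratio. With n = 259 × 0.95 ≈ 246 per arm and α = 0.025, power = Φ(|δ|/(σ√(2/n)) − 2.241).

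- Albumin-to-creatinine ratio: |ln 0.75|/1.0 = 0.2877; 0.2877/√(2/246) = 3.19; Φ(0.95) = 82.9%, against 82% stated.
- eGFR change: 1.65/5.8 = 0.2845; 0.2845/√(2/246) = 3.15; Φ(0.91) = 82.0%, against 81% stated.

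Both agree to about one point, so 518 is a sound basis.

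**Step 1: masking in a single data set (assumed counts).** With x₁ and x₀ patients affected out of n = 259 each and p = (x₁ + x₀)/(2n), χ² = [(x₁ − x₀)/n]² / [p(1 − p)·2/n].

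- Serious bleeds only, 8 vs 1: p = 9/518 = 0.0174; χ² = 0.000730/0.000132 = 5.54; p=0.019 (Fisher p=0.037).
- Add 25 other patients per arm with only minor bleeds, giving 33 vs 26: p = 59/518 = 0.1139; χ² = 0.000730/0.000779 = 0.94; p=0.33.

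The difference is 7/259 = 2.7 percentage points in both lines. Only the variance has grown.

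**Step 2: dependence on the background rate.** Assume serious bleeds in 2.5% (curcumin) vs 0.5% (placebo), and minor bleeds in a fraction m of each arm, independent of serious ones. Then P(any) = 1 − (1 − serious)(1 − m). Power is by exact binomial enumeration of the planned test with 259 per arm.

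| Minor bleeds, m | Any bleed, curcumin vs placebo | Power of planned test |
|---|---|---|
| 0 | 2.5% vs 0.5% | 47% |
| 1% | 3.5% vs 1.5% | 30% |
| 2% | 4.5% vs 2.5% | 23% |
| 3% | 5.4% vs 3.5% | 18% |
| 10% | 12.3% vs 10.5% | 10% |

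**Step 3: what a separate count could detect.** With smaller assumed excesses, a test of serious bleeds alone is also weak: 16% power at 1% vs 0.2%, and 8% at 1% vs 0.5%. Chi-squared is unreliable at such counts: 4 vs 0 gives p=0.045, whereas Fisher's test gives p=0.12.

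**The case against.** The strongest objection is that the SAP is silent rather than wrong. Side effects are recorded on standardized case report forms that are not among the documents, and those forms may set a threshold or record site and severity. A reader might infer that the plan counts bleeds of every severity alike, so that an excess of serious bleeds would be lost. The documents do not support that. The event is undefined, no minor bleed is mentioned, and no background rate is given. What stands is that the SAP gives no definition and no severity breakdown, and that masking could occur if minor bleeds are counted.

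A second objection is that the 47% figure does not measure the value of a separate row. A reader might infer that counting serious bleeds separately restores that power. It does not: the figure belongs to a chi-squared test that is not being requested, at counts where the test is fragile, and under an assumed five-fold excess. Exclusion of warfarin users, active peptic ulcer disease and recent significant bleeding probably lowers the true serious rate. This objection stands in full; the benefit is descriptive.

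Third, there are partial safeguards. The DSMB reviewed safety events (SAP 3.5), unblinding events are summarized by group (SAP 3.2), and deaths and discontinuations are reported by group (SAP 6.1 and 6.4). They make complete loss of a serious signal less likely, but none of them puts a count of serious bleeds by arm into the final report.

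Finally, the Table 1 wording was written for eligibility. Using it as an outcome is a reviewer's proposal, and it is not a complete definition of serious bleeding.

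**Conclusion.** The point holds in a limited form. As planned, the final analysis cannot distinguish serious from minor bleeds by arm, because the event is undefined, severity is not separated, and no other listed analysis fills the gap. If minor bleeds are counted, a serious excess could be masked. How far depends on rates that the documents do not give: at an assumed 2.5% vs 0.5%, power falls from 47% to between about 30% (minor bleeds in 1% of each arm) and about 10% (in 10%). These figures rest on 259 per arm, equal minor bleeding in both arms, and independence of minor and serious bleeds. The primary efficacy conclusions are unaffected. The safety statement carried into a larger trial is what could mislead.

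**What to change.** In SAP 6.4:

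1. State what counts as a bleeding event.
2. Keep the any-bleeding row and its planned test.
3. Add a descriptive row by arm for bleeds after randomization that meet the Table 1 wording (gastrointestinal or retroperitoneal with transfusion, or intracranial of any kind), without the 6-month look-back. Give counts and an exact 95% confidence interval for the difference, with no added test.
4. Classify from the existing event records before unblinding, through the adverse event adjudication that the published protocol (Study Setting) already assigns to the steering committee.

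The cost is one table row and a blinded review of bleeding reports. There are three downsides. Few events are likely, so the interval will be wide. The eligibility wording omits some serious bleeds, for example at other sites or without transfusion. The records must also hold enough detail to classify, which the documents do not confirm; if they do not, the report should say so.

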6.5 Statistical software

SAS software version 9.4 will be used for all analyses.

	Known allergy to ingredients of the study product or placebo [microcrystalline cellulose, vegetarian capsule (carbohydrate gum [cellulose], purified water), vegetable grade magnesium stearate (lubricant), silica]	
	Pregnant or breastfeeding	
	Women of childbearing potential	Operational definition: Women of child bearing potential are those who are not either surgically sterile (bilateral tubal ligation, hysterectomy, bilateral salpingo-oophorectomy) or not postmenopausal for at least 1 year
	Plans for transplantation during the study period	Operational definition: Patients who have completed a transplant recipient work-up or who are active on the renal transplant list
	Receipt of hemodialysis or peritoneal dialysis in the past 3 months	
	Active peptic ulcer disease	Operational definition: Active peptic ulcer disease includes patients who are: i. Currently receiving H.pylori eradication therapy or have received it in the past 30 days (H.pylori eradication therapy is combination therapy with a proton pump inhibitor [lansoprazole 30 mg twice daily, omeprazole 20 mg twice daily, pantoprazole 40 mg twice daily, rabeprazole 20 mg twice daily, or esomeprazole 40 mg once daily], amoxicillin [1 g twice daily], and clarithromycin [500 mg twice daily] for 7 to 14 days) ii. Awaiting upper endoscopy

		(esophagogastroduodenoscopy) for the diagnosis of epigastric pain. iii. Experiencing ulcer-like dyspepsia (moderate to severe epigastric pain that worsens with eating or regularly occurs two to five hours after meals) that is not otherwise diagnosed.
	Hepatobiliary disease in the past 4 weeks (biliary obstruction, cholecystitis)	Operational definition: i. Patients with biliary obstruction includes those with a diagnosis of obstruction ii. Patients with cholecystitis include those with diagnosed cholecystitis and those with suspected cholecystitis (right upper quadrant abdominal pain that may radiate to the back or right shoulder that lasts four to six hours and may be exacerbated by ingestion of fatty foods)
	Evidence of acute kidney injury (>50% increase in serum creatinine in the past 30 days)	
	History of significant bleeding	Operational definition: gastrointestinal or retroperitoneal bleed requiring transfusion, or any intracranial hemorrhage in the last 6 months
	Ongoing use of warfarin	
	Ongoing chemotherapy treatment with cyclophosphamide, camptothecin, mechlorethamine or doxorubicin	
	Ongoing use of anti-psychotic including haloperidol, aripiprazole, risperidone, ziprasidone, pimozide, and quetiapine	
	Previous participation in MPAC-CKD-1	
	Current participation in another investigational medication trial	

Abbreviations: ACE angiotensin converting enzyme; ACR albumin-to-creatinine ratio; ARB angiotensin receptor blocker; CKD chronic kidney disease

Table 2. Pre-randomization/pre-treatment participant characteristics

Participant characteristic	Summary measure
Age at recruitment, years	mean (SD)
Male	n (%)
Height, cm	mean (SD)
Weight, kg	mean (SD)
Body mass index, kg/m ²	mean (SD)
Body mass index categories, kg/m²	n (%)
< 25 kg/m ²	
25-29 kg/m ²	
30-34 kg/m ²	
≥ 35 kg/m ²	
Systolic blood pressure, mmHg	mean (SD)
Diastolic blood pressure, mmHg	mean (SD)
Serum creatinine, µmol/L	mean (SD)
eGFR, mL/min per 1.73m ² ^a	mean (SD)
eGFR categories, mL/min per 1.73m²^a	n (%)
45-60	
30-44	
< 30	
Urinary albumin to creatinine ratio, mg/mmol	mean (SD)
Race/ethnicity	n (%)
White/Caucasian	
Black/African American/African Canadian	
Hispanic/Latino	
Asian (Far East, Southeast Asia, Indian Subcontinent)	
Middle East	
Aboriginal/Native Persons/American Indian	
Other	
Diabetes	n (%)
HbA1c	mean (SD)
Insulin use	n (%)
Oral hypoglycemic	
Insulin or oral hypoglycemic	
History of smoking	n (%)
Current	
Remote ^b	
No	
Primary cause of CKD	n (%)
Diabetic nephropathy	
Glomerulonephritis	
Hypertensive nephrosclerosis	
Polycystic kidney disease	
Other	
Medication use	n (%)
ACE inhibitors	
Angiotensin II receptor blockers (ARBs)	
ACE inhibitors or ARBs	
Diuretics	
Calcium channel blockers	
Beta blockers	
Aspirin	
Antiplatelet drugs (not including aspirin)	
Anti-inflammatories (regularly scheduled use)	
Oral glucocorticoids	
Cholesterol lowering medications (niacin, fibrates, statins)	
Opioid analgesic	

Non-warfarin anticoagulant	
----------------------------	--

^a CKD-EPI eGFR equation.³⁴

^b Smoker within the last 10 years, but not currently smoking.

Micro-Particle Curcumin for the Treatment of Chronic Kidney Disease-1 (MPAC-CKD-1)

Statistical Analysis Plan (SAP)

Supplemental Document

Supplemental Table 1. Changes to the published MPAC-CKD-1 protocol ([name] et al. *Can J Kidney Health Dis.* 2018;5:1-9)

Published protocol	Change in SAP	Reason for change
“Using these data, enrolling 250 patients per group will allow an 87% power ($\alpha=0.025$) to exclude a difference of 21 mg/mmol. To allow for loss to follow-up, we expect to recruit up to an additional 75 patients to reach a minimum of 250 patients per arm with complete follow-up data.”	“Enrolling a total of 518 patients and accounting for 5% loss to follow-up allows for 82% power ($\alpha = 0.025$) to detect a geometric mean ratio of 0.75, assuming a standard deviation of the 6-month log-transformed albumin-to-creatinine ratio of 1.0”	We will follow the recently published methods used by Heerspink et al. (Lancet Diabetes Endocrinol. 2019;7:128-39) for between-group comparisons involving albumin-to-creatinine data. These methods were published after the creation of our original protocol. We have updated our sample size calculations to reflect this.
“For changes in eGFR, we will have 90% power ($\alpha = 0.025$) to exclude a difference of 2.3 mL/min/1.73m ² between treatment and control groups (using a standard deviation of 4 mL/min/1.73m ²).”	“For the between-group difference in change in eGFR (6-month eGFR minus pre-randomization eGFR), we will have 81% power ($\alpha = 0.025$) to exclude a difference of 1.65 mL/min per 1.73 m ² between treatment and control groups (using a standard deviation of the change of 5.8 mL/min per 1.73 m ²).”	We have updated our sample size calculations using the overall standard deviation of the change in eGFR in the MPAC-CKD-1 study (without any by-group computations); we have also updated the detectable between-group difference to more closely align with observed effects in Inker et al. (J Am Soc Nephrol. 2019;30:1735-1745).
“We will use two-sample t tests to compare changes in the co-primary outcomes.”	“The geometric mean ratio of 6-month urinary albumin-to-creatinine ratio will be estimated using linear regression, where the outcome is the log-transformed average of two 6-month follow-up visit urinary albumin-to-creatinine ratio measurements minus log-transformed average of two pre-treatment urinary albumin-to-creatinine ratio measurements, adjusting for a treatment indicator variable and the log-transformed average of two baseline urinary albumin-to-creatinine ratio measurements.”	We will follow the recently published methods used by Heerspink et al. (Lancet Diabetes Endocrinol. 2019;7:128-39) for between-group comparisons involving albumin-to-creatinine data. These methods were published after the creation of our original protocol. We have also updated the planned method of analysis for the outcome of change in eGFR; linear regression will be used instead of a t -test. We expect that the estimates and P values will be virtually identical in both methods (linear regression vs. t -test).
“We will use a two-sample t test to compare changes in hemoglobin A1c between the 6-month and baseline values. The risk of the composite outcome of loss of $\geq 30\%$ of baseline eGFR, ESRD, or death will be compared between groups using logistic regression analysis. The proportions of patients discontinuing study capsules and experiencing adverse events will be compared between groups using the chi-square test.”	Estimates of between-group differences in the secondary outcomes will be presented with 95% confidence intervals, without formal hypothesis testing and reporting of P values, in order to reserve the overall type I error rate of 0.05 for the two primary outcomes. Hypothesis tests for between-group differences in safety-related outcomes will be tested at the 0.05 significance level. The safety-related outcomes are: (i) minor side-effects including minor nausea, headache, diarrhea, yellow stool, temporary giddiness, localized swelling of the skin, or hives; (ii) bleeding; (iii) hypoglycemia.	These changes are in accordance with new guidelines regarding multiple testing and adjustment for multiplicity in Harrington et al. (N Engl J Med. 2019;381:285-286). Hypothesis tests for outcomes related to safety will be performed according to New England Journal of Medicine publication guidelines. (https://www.nejm.org/author-center/new-manuscripts)


“We will record baseline characteristics pertinent to the progression of CKD and adjust the final point estimates of risk for these variables using linear regression analysis. Characteristics that will be included in the multivariable regression model are the following: age, sex, tobacco use, blood pressure, glycemic control, use of angiotensin-converting enzyme inhibitors or angiotensin receptor blockers, use of aldosterone antagonists.”
	
“In sensitivity analyses, we will repeat the two primary analyses while (i) accounting for randomization strata (centre and pre-randomization diabetes); (ii) accounting for randomization strata and adjusting for variables associated with disease progression including age, sex, tobacco use, blood pressure, baseline use of angiotensin-converting enzyme inhibitors or angiotensin receptor blockers, and baseline use of aldosterone antagonists.”
	
We have updated the planned sensitivity analyses to account for randomization strata, with and without adjustment for baseline characteristics. We do not anticipate that accounting for randomization strata and/or adjustment for pre-randomization variables will change results in any meaningful way.

“To confirm the improved bioavailability reported with micro-particle curcumin, and to strengthen any relationship between micro-particle curcumin and any outcomes we identify, we will measure serum trough levels of curcumin and its major metabolites in the first 25 participants randomized.”
	
“To confirm our micro-particle curcumin was bioavailable, and to strengthen any relationship between micro-particle curcumin and any outcomes we identify, serum levels of curcumin and its major metabolites were measured in the first 30 participants 3 months after randomization (including patients taking micro-particle curcumin and those taking placebo).”
	
Serum curcumin and its major metabolites were collected in the first 30 patients randomized; the measurements were not necessarily taken prior to treatment (the values are not necessarily trough levels).

The published protocol contained general information on inclusion and exclusion criteria.
	
The SAP includes detailed information on inclusion/exclusion criteria.

